#### **10.9.3 Case Processing and Submission to Competent Authorities**

In accordance with GVP Module VI.C.1.2.1.2 (non-interventional post-authorization studies with a design based on secondary use of data) the submission of suspected ADRs in the form of individual case safety reports (ICSRs) is not required. Therefore, Allergan will not submit any ICSRs for solicited ADRs collected for the study. However, all AEs/ADRs collected for the study will be recorded in the study database and summarized in study reports.

The investigators are responsible for maintaining compliance with any applicable site-specific requirements related to the reporting of SAEs or other safety information to the local IEC that approved the study.

## **11 DATA SOURCES**

This is a retrospective, observational study, and patient data collected from the sites will be abstracted from medical charts.

## 12 DATA MANAGEMENT

All data collected in the context of this study will be stored and evaluated in accordance with regulatory requirements and applicable guidance for electronic records.

Electronic data collection will be performed using an e-CRF. Investigators or study personnel will enter data into the electronic data capture (EDC) system according to the schedule of assessments (Table 2) and according to instructions from the Sponsor and/or designee. Only authorized personnel will have access to the EDC system. Data will be anonymized and once entered in the system, investigators and study personnel will not be able to identify patients.

Each investigator is responsible for ensuring that accurate data are entered into the EDC system in a timely manner. Specific processes used to manage the data throughout the study will be documented in the Data Management Plan. Briefly, on-line logic checks will be built into the system, so that missing or illogical data are not submitted. In the event that inconsistent data persist, no queries will be issued as investigators will not be able to connect the patient with his/her identification number. Consequently, to prevent as much as possible remaining inconsistent data, all data entered into the eCRF should be reviewed by the principal investigator. The principal investigator will be responsible for endorsing data within the eCRF. This approval method will include applying an electronic signature, a uniquely assigned user name, and a password that together will represent a traditional handwritten signature.

Medical history, concomitant disease, and AEs will be coded, using Medical Dictionary for Regulatory Activities (MedDRA, the most recent version). Drugs will be coded with the WHO Drug Dictionary.

A final validation of the database will be performed, and the database will be locked, before the statistical analysis is conducted.

## 13 QUALITY CONTROL

Designated study personnel will participate in a training program that will encourage consistency of process and procedures at the investigative site and ensure collection of high-quality data for this study. All sites will be trained on the protocol, study logistics, and the EDC system. Retraining will be conducted as needed.

The Sponsor and its representatives will monitor the study over the telephone on a regular basis, according to the Monitoring Plan. At the monitoring visits, the progress of the study and any procedural or data issues will be discussed with the site and/or designee (see Section 9.1.3).

Quality controls performed during statistical analyses will be described in the statistical analysis plan (SAP).

Secure electronic archive will be maintained and will include but will not be limited to: final raw data, analysis datasets, programs and associated documentation. Access to the archive will be controlled and limited to authorized personnel only.

## 14 STATISTICAL METHODS

### 14.1 Sample Size

The study aims to select 150 patients. As study primary objective is to assess reinjection interval of Ozurdex implant in real-world, sample size calculations were performed to evaluate the precision around the mean of the reinjection interval.

Few data were published on the reinjection interval in patients diagnosed with diabetic macular edema in real-world. Matropasqua et al. reported a mean  $\pm$  standard deviation (SD) of  $6.7 \pm 2.3$  months in 27 Italian patients. Querques et al. reported a mean of 4.9 and 4.7 months from respectively 570 French patients of a pharmacist database and 114 patients from the French Social Security database (no standard deviations were available). The same study also reported a mean ( $\pm$ SD) of  $4.8 \pm 1.8$  months between reinjections based on data from 111 French ophthalmologists who completed a survey about their practice.

The precision of the 95% confidence interval (CI) of the mean ( $\omega$ , half of the width of the CI) is determined using the following formula:

$$\omega = \frac{1.96 \times SD}{\sqrt{n}}, \text{ where SD is the standard deviation and } n \text{ is the sample size.}$$

Table 4 shows the precision and 95% CI of the mean considering a SD ranging from 1.5 to 3.0 and a sample size of 150 patients.

**Table 4 Precision and 95% CI of the mean considering a standard deviation ranging from 1.5 to 3.0, a mean ranging from 4.7 to 6.7 and a sample size of 150 patients**

SD	Mean (month)				
	$\omega$	4.7	5.5	6.0	6.7
1.5	0.2	4.5-4.9	5.3-5.7	5.8-6.2	6.5-6.9
2.0	0.3	4.4-5.0	5.2-5.8	5.7-6.3	6.4-7.0
2.5	0.4	4.3-5.1	5.1-5.9	5.6-6.4	6.3-7.1
3.0	0.5	4.2-5.2	5.0-6.0	5.5-6.5	6.2-7.2

Considering SD of the mean reinjection interval ranging from 1.5 to 3 months, the selection of 150 patients will enable the description of a mean reinjection interval with precision ranging from 0.2 to 0.5 months, i.e. 6 to 15 days (worst case).

For example, for a mean interval between two Ozurdex injections of 6.0 months, the 95% CI of the mean would be 6.0 [5.5-6.5] months in the worst case (i.e., 183 days [168-198],  $\omega = 15$  days).

 Standard deviation was not clearly available in the paper and was recalculated from available data.

A secondary objective of the study is to assess drug effectiveness in a subgroup of patients who are naïve of any anti-VEGF treatment. One of the outcomes of interest for this subgroup of patients will be the change in BCVA from the first injection to 7-12 weeks following each reinjection.

In 2015 Escobar-Barranco et al reported a difference in visual acuity from baseline to 6 months (mean  $\pm$  SD) of  $11.5 \pm 4.6$  ETDRS letters in 36 treatment naïve patients whereas in 2018 Iglicki et al. reported a gain at 24 months (mean  $\pm$  SD) of  $11.3 \pm 10.0$  letters in 71 eyes of treatment naïve patients.

The precision and 95% CI of the mean have been calculated considering a mean gain of 11.5 letters, standard deviation ranging from 4.5 to 10.0 and a sample size of 50 patients (Table 5).

**Table 5 Precision and 95% CI of the mean considering a mean gain of 11.5 letters, a standard deviation ranging from 4.5 to 10.0 and a sample size of 50 patients**

SD	$\omega$	95% CI
4.5	1.3	10.2-12.8
6.0	1.7	9.8-13.2
8.0	2.2	9.3-13.7
10.0	2.8	8.7-14.3

Considering SD ranging from 4.5 to 10.0, a subgroup of 50 patients who are treatment naïve will enable to describe a mean change in visual acuity with precision ranging from 1.3 to 2.8. For example, for a mean change in visual acuity of 11.5, the 95%CI of the mean will be 11.5 [8.7-14.3] letters in the worst case. It has been considered as satisfactory for this secondary objective.

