### 8.2 Patients

From a public health and market access perspective, the present study population constitutes a broader real-world patient population than that reflected in clinical trials. The present study design cannot make any conclusions on causal relationships, but can rather explore real-world Ozurdex drug utilization patterns, effectiveness and safety. It is expected that the results from this study may be generalizable to the overall population presenting with DME and treated with Ozurdex in Germany and Switzerland.

Patients may contribute at most one eye into the study. If both eyes meet the inclusion criteria, the eye that received the most Ozurdex injections will be chosen as the study eye.

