## **9 STUDY PROCEDURES**

### **9.1 Site Selection, Enrollment and Training**

#### **9.1.1 Sampling**

Allergan will identify sites among experienced medical retina centers treating DME patients. Sites will be identified using Allergan field-based knowledge.

The study will be proposed to all the sites identified by Allergan; a recruitment mail containing the study summary, the site qualification questionnaire and a reply coupon will be sent to all these sites. If the return rate is insufficient, non-responders will be contacted by telephone to fill out the site qualification questionnaire.

The Sponsor or designee will qualify sites with sufficient resources (time, personnel, and facilities) to participate in the study. Sites will be required to obtain approval from the appropriate Independent Ethics Committee (IEC), and will be responsible for maintaining all related documents, before enrollment of any patient into the study.

Recruitment will end as soon as approximately 10 sites, 7 in Germany and 3 in Switzerland, are qualified to participate in the study.

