## **15.0 ANALYSES OF THE OBJECTIVES OF THE STUDY**

### **15.1 ANALYSIS OF THE PRIMARY OBJECTIVE**

The primary objective '*To assess reinjection interval of Ozurdex implants in patients with DME in real-world in Germany and Switzerland*' will be assessed by the following outcomes:

- Total number of Ozurdex reinjections in the study eye during follow-up, and considering years after the first Ozurdex injection in the study eye (See definition in Table 21-1).
- Re[injection interval defined in months as: (Date of injection (j+1) – Date of injection j) ÷ (365.25÷12), for j=1,...,n where n is the number of reinjections in the study eye. The result will be rounded to 0.1.

The number of Ozurdex reinjections in the study eye per year will be first summarized using descriptive statistics for the following parameters:

- The total number and percentage of Ozurdex reinjections received during follow-up.
- Number and percentage (with 95% CI) of patients with at least one Ozurdex reinjection during Year 1 (See definition in Table 21-1), and number of reinjections per patient during Year 1, for all patients in the analysis population. Note: the first Ozurdex injection will not be considered here, only reinjections will be counted.
- Number and percentage (with 95% CI) of patients with at least one Ozurdex reinjection and number of reinjections per patient during Year k (k=2, 3), for patients having a complete Year k of follow-up (see definition of 'Complete year' in Section 21.2).
- Number and percentage of patients receiving each Ozurdex reinjection (first, second, third, etc) for each year of follow-up (Year k, k=1 to 3) considering patients having the complete year of follow-up.

The Ozurdex reinjection interval in the study eye will be described using descriptive statistics for the following parameters:

- Re[injection interval (months) considering all eligible reinjections recorded in the EDC. The 95% CI of the mean will also be presented.
- Re[injection interval (months) considering each reinjection separately (i.e. first reinjection, second reinjection, etc). 95% CI of the mean will also be presented.

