### Confidence intervals

Confidence intervals for means and exact confidence intervals (Clopper-Pearson) for percentages will be calculated when appropriate and will be 2-sided at the 95% level.

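### The stated precision of 0.2 to 0.5 months and the planned 95% CIs of the mean reinjection interval ignore clustering by site and, in the overall CI, repeated intervals within a patient

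*Protocol*

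**What the plan says.** Protocol 14.1 sets the size of the study by precision: "The study aims to select 150 patients", with the half-width of the 95% CI computed as 1.96 x SD / sqrt(n). Table 4 does this "considering a SD ranging from 1.5 to 3.0 and a sample size of 150 patients", and the text concludes that "the selection of 150 patients will enable the description of a mean reinjection interval with precision ranging from 0.2 to 0.5 months", which it converts to 6 to 15 days. SAP 19.0 repeats the formula, table and conclusion.

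Protocol 9.1.1 describes where the patients come from: "Recruitment will end as soon as approximately 10 sites, 7 in Germany and 3 in Switzerland, are qualified to participate in the study". Under Protocol 9.2, the number of patients at each site is set from feasibility surveys and consultation with the sponsor, so site sizes need not be equal.

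SAP 15.1 describes the reinjection interval in two ways: over all eligible reinjections together, and separately for each reinjection number. For the former it says "The 95% CI of the mean will also be presented", and it plans the same for the latter. The only further instruction is in SAP 21.1: intervals for means "will be 2-sided at the 95% level". Neither document gives a design effect, an ICC, a site term, a cluster-robust variance or a patient-level random effect. The only geographic analysis is the Germany versus Switzerland subgroup in SAP 6.3.

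On the target of inference, Protocol 8.2 states: "It is expected that the results from this study may be generalizable to the overall population presenting with DME and treated with Ozurdex" in the two countries.

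**The concern.** An ordinary CI of a mean is valid when its observations are independent. Here there are two reasons to doubt that.

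- **Site.** Patients are sampled within about 10 centres. The outcome is the timing of a treatment decision in routine practice, so patients of one centre may have more similar intervals than patients of different centres. This applies even with one interval per patient.
- **Patient.** The overall CI counts every interval as a separate observation. A patient with several reinjections contributes several intervals, which may be correlated.

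Positive correlation at either level makes the true standard error larger than the computed one. The mean interval with its 95% CI is a main primary result, and its precision is the stated basis for 150 patients. If the results are meant to describe patients beyond the participating centres, variation between centres belongs in the error bar.

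**Working it through.** **Inputs**

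- n = 150; SD 1.5 to 3.0 months; multiplier 1.96 (Protocol 14.1, SAP 19.0).
- About 10 sites (Protocol 9.1.1), so m = 150/10 = 15 patients per site on average.
- 1 month = 30.4375 days (SAP 21.3.4).
- Site ICC: not in the documents; assumed from 0 to 0.20.

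**Step 1: reproduce the plan.** Half-width = 1.96 x SD / sqrt(150).

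- SD 1.5: 0.240 months; SD 2.0: 0.320; SD 2.5: 0.400; SD 3.0: 0.480 (14.6 days).

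Table 4 is arithmetically right under independence.

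**Step 2: add site clustering, one interval per patient.** Design effect DE = 1 + (m - 1) x ICC = 1 + 14 x ICC. Half-width = 1.96 x SD x sqrt(DE / 150). The last column is the approximate coverage of a nominal 95% CI that ignores site, 2 x Phi(1.96 / sqrt(DE)) - 1.

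| Assumed ICC | DE | Effective n | Half-width, SD 1.5 | Half-width, SD 3.0 | Coverage if site ignored |
|---|---|---|---|---|---|
| 0 | 1.00 | 150 | 0.24 | 0.48 (14.6 days) | 95% |
| 0.02 | 1.28 | 117 | 0.27 | 0.54 (16.5 days) | 92% |
| 0.05 | 1.70 | 88 | 0.31 | 0.63 (19 days) | 87% |
| 0.10 | 2.40 | 62.5 | 0.37 | 0.74 (23 days) | 79% |
| 0.20 | 3.80 | 39 | 0.47 | 0.94 (28 days) | 69% |

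The SD 3.0 half-width stops rounding to 0.5 when it reaches 0.55, that is, when ICC = ((0.55 / 0.480)^2 - 1) / 14, about 0.022.

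These figures apply to the planning calculation and, at most, to the CI for the first reinjection. Later reinjections may involve fewer patients.

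**Step 3: two features that widen the interval further (SD 3.0).**

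- With about 10 clusters, t on 9 df replaces 1.96. The half-width is then 0.72 at ICC 0.05 and 0.86 at ICC 0.10. At ICC 0 it is 0.55.
- Unequal sites, with an assumed coefficient of variation of site size of 0.5: DE = 1 + ((0.5^2 + 1) x 15 - 1) x ICC. This gives 0.66 at ICC 0.05 and 0.80 at ICC 0.10 (multiplier 1.96).

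**Step 4: the overall CI, which pools intervals.** Let k be the intervals per patient, r the correlation between intervals of one patient, and ICC the site correlation. Then DE = 1 + (k - 1) x r + 14 x k x ICC, applied to the variance with 150 x k observations. Assume k = 3, r = 0.5 and SD 3.0.

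- Both levels ignored: 1.96 x 3.0 / sqrt(450) = 0.28 months.
- Patient level only: DE = 1 + 2 x 0.5 = 2.0, half-width 0.39.
- Site ICC 0.05 added: DE = 1 + 1 + 14 x 3 x 0.05 = 4.1, half-width 0.56.

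In this illustration the reported CI would be about half as wide as it should be (0.28 / 0.56). The values of k and r are assumptions; the documents give neither.

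**The case against.** The strongest reply is that the plan measures nothing about clustering, so a shortfall cannot be asserted as fact. No ICC is given. At ICC 0.02 the worst row still rounds to 0.5, and at 0.05 it adds about 4 days to the stated 15. Protocol 15.3 says treatment follows clinical judgment, and SAP 15.2.2 lists disease progression and lack of effect among the reasons for reinjection. Nothing says that the centre sets the interval. All of this stands, and it is why the size is given as a range that includes no effect.

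Other points on that side:

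- **Worst case.** In Protocol 14.1 the phrase refers to the largest SD in the table. It does not promise that no other source of error exists. A reader might infer that the plan misstates its own table; it does not.
- **Unit of the overall CI.** A reader might infer that this CI treats 150 patients as independent. SAP 15.1 uses all intervals, so its n is the number of intervals. The 150-patient wording fits the planning formula and, at most, the first-reinjection CI.
- **Survey SD.** Protocol 14.1 cites 4.8 ± 1.8 months "based on data from 111 French ophthalmologists who completed a survey about their practice". A reader might infer that it was used as a patient-level SD, or that it shows how much sites differ. Neither is supported. It is cited beside a patient SD of 2.3, and 1.8 is not a row of Table 4. It is the reported practice of individual French physicians, with an SD that the sponsor recalculated, and does not measure variation between German and Swiss hospital centres. Taken as a between-site SD against a total of 2.3, it would imply an ICC of 1.8^2 / 2.3^2 = 0.61, for which the documents give no ground.
- **Acknowledgement.** Protocol 7.3.1.1 and 7.3.2 name volunteer-site bias and differing measurement methods across sites. That is fair disclosure, but neither enters the precision or the CI.
- **Descriptive study.** Protocol section 6 states that the objectives rest on no hypothesis. No test or decision depends on the CI, and this lowers the severity.

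**Conclusion.** The point holds as one of overstated precision. The planning formula and the planned CIs assume an independence that the sampling does not provide. The per-reinjection CIs ignore site; the overall CI ignores both site and patient.

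The size is conditional. With SD 3.0, 10 equal sites and multiplier 1.96, the half-width runs from 0.48 months at ICC 0 to 0.94 at ICC 0.20. It leaves the stated 0.5 once the ICC passes about 0.022. Unequal sites, or a t multiplier suited to 10 clusters, make it larger. The point estimate is not affected, and the documents do not show which ICC applies. This is a should-fix item.

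**What to change.** **SAP 15.1.** Keep the point estimate as it is, the mean of the intervals, overall and for each reinjection. Take its 95% CI from a robust standard error clustered on site, with a small-sample correction and t on (sites - 1) df. Because patients are nested within sites, this also covers repeated intervals within a patient. It leaves the estimated quantity unchanged, whereas a mixed model could reweight sites and patients. Report the between-site SD descriptively, which is informative in a drug utilization study.

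**Protocol 14.1 and SAP 19.0.** Label 0.2 to 0.5 months as assuming independent patients. Add the half-widths with DE = 1 + (m - 1) x ICC, m about 15, over a stated ICC range.

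**Cost.** Some wording and a few lines of code; no new patients or data. SAP 8.0 already plans to summarise patients per physician, so the grouping information should be available despite anonymisation; this needs confirming at site level. The CIs will generally be wider and the stated precision less favourable. Even at ICC 0, t on 9 df gives about 0.55 in place of 0.48 months. The standard error will rest on only about 10 clusters and will itself be imprecise. Sites are volunteers identified by the sponsor, and no CI of this kind corrects for that selection.

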Patient Population and Key Selection Criteria	Male and female patients, aged $\geq 18$ years, who received at least 2 Ozurdex implant in the same eye to treat visual impairment due to DME. Among these patients, sites will also be requested to do their best to select a subgroup of up to 50 patients that are naïve to anti-VEGF treatment prior to first Ozurdex implant injection. Patients may contribute at most one eye into the study. If both eyes meet the inclusion criteria, the eye that received the most Ozurdex injections will be chosen as the study eye.
Sample Size	The study aims to select 150 patients. As study primary objective is to assess reinjection interval in real-world, sample size calculation were performed to evaluate the precision around the mean of the reinjection interval.  Considering standard deviations ranging from 1.5 to 3, the selection of 150 patients will enable the description of a mean reinjection interval with satisfactory precisions (half of the 95% confidence interval) ranging from 0.2 to 0.5 months, i.e. from 6 to 15 days (worst case).
Outcome Variables and Assessments	
Ozurdex Real-word Utilization
 
 
Number of Ozurdex implant injections per year
 
Time between Ozurdex implants injections
 
 
Effectiveness:
 
 
Best-corrected visual acuity (BCVA) change from time of injection to 7–12 weeks following each Ozurdex implant injection
 
BCVA change from time of first Ozurdex implant injection to 7–12 weeks following each Ozurdex implant injection
 
Central retinal thickness (CRT) by optical coherence tomography (OCT) change from time of injection to 7–12 weeks following each Ozurdex implant injection
 
CRT by OCT change from time of first Ozurdex implant injection to 7–12 weeks following each Ozurdex implant injection
 
 
Safety:
 
 
Number and percentage of patients who experienced AESIs
 
[REDACTED]
 
[REDACTED]
 

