## **19.0 DETERMINATION OF SAMPLE SIZE**

The study aims to select 150 patients. As study primary objective is to assess reinjection interval of Ozurdex implant in real-world, sample size calculations were performed to evaluate the precision around the mean of the reinjection interval.

Few data were published on the reinjection interval in patients diagnosed with DME in real-world. Matropasqua et al. reported a mean  $\pm$  standard deviation (SD) of  $6.7 \pm 2.3$  months in 27 Italian patients. Querques et al. reported a mean of 4.9 and 4.7 months from respectively 570 French patients of a pharmacist database and 114 patients from the French Social Security database (no standard deviations were available). The same study also reported a mean ( $\pm$ SD) of  $4.8 \pm 1.8$  months between reinjections based on data from 111 French ophthalmologists who completed a survey about their practice.

The precision of the 95% CI of the mean ( $\omega$ , half of the width of the CI) is determined using the following formula:

$$\omega = \frac{1.96 \times SD}{\sqrt{n}}, \text{ where SD is the standard deviation and } n \text{ is the sample size.}$$

Table 18-1 shows the precision and 95% CI of the mean considering a SD ranging from 1.5 to 3.0 and a sample size of 150 patients.

**Table 18-1 Precision ( $\omega$ ) and 95% CI of the mean considering a standard deviation ranging from 1.5 to 3.0, a mean ranging from 4.7 to 6.7 and a sample size of 150 patients**

SD	Mean (months)				
	$\omega$	4.7	5.5	6.0	6.7
1.5	0.2	4.5-4.9	5.3-5.7	5.8-6.2	6.5-6.9
2.0	0.3	4.4-5.0	5.2-5.8	5.7-6.3	6.4-7.0
2.5	0.4	4.3-5.1	5.1-5.9	5.6-6.4	6.3-7.1
3.0	0.5	4.2-5.2	5.0-6.0	5.5-6.5	6.2-7.2

Considering SD of the mean reinjection interval ranging from 1.5 to 3 months, the selection of 150 patients will enable the description of a mean reinjection interval with precision ranging from 0.2 to 0.5 months, i.e. from 6 to 15 days (worst case).

For example, for a mean interval between two Ozurdex injections of 6.0 months, the 95% CI of the mean would be 6.0 [5.5-6.5] months in the worst case (i.e., 183 days [168-198],  $\omega = 15$  days).

A secondary objective of the study is to assess drug effectiveness in a subgroup of patients who are naïve of any anti-VEGF treatment. One of the outcomes of interest for this subgroup of patients will be the change in BCVA from the first injection to 7-12 weeks following each reinjection.

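### Two best-case precision figures do not follow from the plan's own formula: 6 days should read 7, and 1.3 letters at SD 4.5 should read 1.2

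*Protocol*

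**What the plan says.** Protocol 14.1 bases the sample size on precision alone. It states "The study aims to select 150 patients" and then defines ω as half the width of the interval: "The precision of the 95% confidence interval (CI) of the mean" is obtained as ω = 1.96 × SD / √n.

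- **Primary mean.** The text opens with "Considering SD of the mean reinjection interval ranging from 1.5 to 3 months" and concludes "precision ranging from 0.2 to 0.5 months, i.e. 6 to 15 days (worst case". Table 4 prints ω of 0.2, 0.3, 0.4 and 0.5 months for SDs of 1.5, 2.0, 2.5 and 3.0. The synopsis gives the same range, "ranging from 0.2 to 0.5 months, i.e. from 6 to 15 days (worst case", and describes the precision as satisfactory. SAP 19.0 repeats it: "precision ranging from 0.2 to 0.5 months, i.e. from 6 to 15 days (worst case".
- **Anti-VEGF-naïve subgroup.** For a mean gain of 11.5 letters, n = 50 and SDs of 4.5 to 10.0, Protocol Table 5 and SAP Table 18-2 print ω of 1.3, 1.7, 2.2 and 2.8. The first row's CI is 10.2–12.8. Both documents summarise this as "precision ranging from 1.3 to 2.8".

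**The concern.** The formula and all its inputs are printed, so a reader can check each figure in a minute. The lower end of each range fails that check. The study tests no hypothesis (Protocol 6), so these half-widths are the only quantitative support offered for 150 patients and for a subgroup of 50. The synopsis also attaches a judgement of adequacy to the range in days. What is at stake is the accuracy of stated numbers in that justification, carried unchanged from the Protocol into the SAP. The size of the study is not at stake.

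**Working it through.** **Inputs**

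- Formula: ω = 1.96 × SD / √n (Protocol 14.1; SAP 19.0).
- Primary mean: n = 150, SD 1.5 to 3.0 months (Protocol 14.1).
- Naïve subgroup: n = 50, SD 4.5 to 10.0 letters, mean gain 11.5 (Protocol 14.1; SAP 19.0).
- Conversion: 1 month = 30.4375 days (SAP 21.3.4). The Protocol's worked example agrees: 6.0 × 30.4375 = 182.6, printed as 183 days.

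**Primary mean, √150 = 12.247**

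| SD (months) | 1.96 × SD / √150 (months) | Printed (months) | In days |
|---|---|---|---|
| 1.5 | 2.94 / 12.247 = 0.240 | 0.2 | 7.3 |
| 2.0 | 3.92 / 12.247 = 0.320 | 0.3 | 9.7 |
| 2.5 | 4.90 / 12.247 = 0.400 | 0.4 | 12.2 |
| 3.0 | 5.88 / 12.247 = 0.480 | 0.5 | 14.6 |

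Every ω in Table 4 reproduces to one decimal, and so does the upper end of 15 days. The lower end does not: 0.240 × 30.4375 = 7.3 days. A 30-day month gives 7.2 days, and a t quantile in place of 1.96 gives 7.4. Six days appears only when the rounded value is converted: 0.2 × 30.4375 = 6.1. The upper end survives this order of rounding because 0.480 months (14.6 days) and 0.5 months (15.2 days) both round to 15.

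**Naïve subgroup, √50 = 7.071**

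| SD (letters) | 1.96 × SD / √50 | Printed ω | 11.5 ± ω | Printed CI |
|---|---|---|---|---|
| 4.5 | 8.82 / 7.071 = 1.247 | 1.3 | 10.25–12.75 | 10.2–12.8 |
| 6.0 | 11.76 / 7.071 = 1.663 | 1.7 | 9.84–13.16 | 9.8–13.2 |
| 8.0 | 15.68 / 7.071 = 2.217 | 2.2 | 9.28–13.72 | 9.3–13.7 |
| 10.0 | 19.60 / 7.071 = 2.772 | 2.8 | 8.73–14.27 | 8.7–14.3 |

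Only the first row fails. To three decimals its limits are 10.253 and 12.747, so the row should read 1.2 (10.3–12.7).

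**Possible sources of the 1.3**

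- SD 4.6, the value Protocol 14.1 quotes from the study of 36 treatment-naïve patients, gives 9.016 / 7.071 = 1.275. That prints as 1.3 with CI 10.2–12.8 and matches the row exactly.
- Rounding twice (1.247 to 1.25 to 1.3) gives the same ω.
- n = 49 gives 1.260, 1.680, 2.240 and 2.800, which fits all four printed ω values, but the plan states 50.
- A t quantile gives 1.279 at SD 4.5 but 2.274 at SD 8, which would print as 2.3 where the table has 2.2. It does not explain the table.

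The documents do not show which of the first three applies.

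**The case against.** The best defence is that the formula was applied correctly to the primary mean and precision was lost only in display. Table 4's 0.2 is the correct rounding of 0.240, and 6 days is a faithful conversion of the printed 0.2. That stands as an account of how the figure arose. It does not make 6 days the result of the formula.

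The defence is also right on materiality. The 150 and the 50 are fixed inputs at which precision was evaluated. The worked examples rest on the worst case, which reproduces. The error in letters is on the cautious side.

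A reader might go further in two ways that the documents do not support:

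- **That the study is too small.** A half-width of 6 days at SD 1.5 would need (1.96 × 1.5 × 30.4375 / 6)² ≈ 222 patients. But nowhere do the documents set 6 days as a target, so no shortfall follows.
- **That the design will deliver worse precision than promised.** The formula counts one interval per patient. SAP 15.1 computes the overall mean and its CI from all eligible reinjections, so patients with several reinjections contribute several intervals, which may be correlated. The resulting precision could be better or worse than 7.3 days, and nothing in the documents settles which.

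**Conclusion.** Both figures are wrong as written under the plan's own formula, sample sizes and SDs. For the primary mean the best case is 7.3 days, not 6: a gap of 1.3 days (one day once rounded), so the printed figure is about 18% below the computed one. For the naïve subgroup the best case is 1.247 letters, not 1.3, a difference of 0.05. The sample sizes and the worst-case figures (15 days; 2.8 letters, CI 8.7–14.3) stand.

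This rests on the SAP's month length, which barely matters, and on the table's SD of 4.5 being the intended value. It is an editorial correction to the sample-size justification and no estimate or analysis changes.

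**What to change.** 1. In the Protocol synopsis, Protocol 14.1 and SAP 19.0, give the primary precision as 0.24 to 0.48 months, equal to 7 to 15 days. Changing only the days would leave 0.2 months set equal to 7 days, which is a new mismatch, so the months need two decimals as well.
2. In Protocol Table 5 and SAP Table 18-2, change the first row to ω = 1.2, CI 10.3–12.7, and change the summary sentence below each table to a range of 1.2 to 2.8.
3. Before making change 2, the sponsor should check its calculation. If SD 4.6 was used, keep 1.3 (10.2–12.8) and instead replace 4.5 by 4.6 wherever the SD or its range is stated: the row, both captions, the Protocol's List of Tables, and the sentences before and after each table in Protocol 14.1 and SAP 19.0.

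The cost is a text correction in two documents. Design, data collection and analysis stay as they are.
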